**Table 3. Power Analysis for the Primary Outcome Variables**

Number of Probe Sets to Examine		1000				2000			
Number of Probe Sets to Detect		10	50	100	300	10	50	100	300
Sample Size	Power	Effect Size							
40 per group	90%	1.1	1.0	0.9	0.8	1.2	1.0	1.0	0.9
	80%	1.0	0.9	0.8	0.7	1.1	1.0	0.9	0.8
	70%	1.0	0.8	0.8	0.7	1.0	0.9	0.8	0.7
60 per group	90%	0.9	0.8	0.8	0.7	0.9	0.8	0.8	0.7
	80%	0.8	0.7	0.7	0.6	0.9	0.8	0.7	0.7
	70%	0.8	0.7	0.6	0.5	0.8	0.7	0.7	0.6

**Table 4. Power Analysis for the Secondary Outcome Variables**

Power	Sample size per group for 2-sided 2-sample t-test			Sample size for 2-sided paired t-test		
	40	50	60	40	50	60
	Effect Size			Effect Size		
70%	0.562	0.502	0.457	0.403	0.358	0.326
80%	0.634	0.566	0.516	0.454	0.404	0.368
90%	0.734	0.665	0.597	0.526	0.468	0.425

## B. Inclusion and Exclusion Criteria

1. Describe the **characteristics and provide justification** for inclusion of the proposed subject population. At a minimum include information about the age and gender of the study population.
2. Describe **different subject groups** (e.g., students and teachers; control group and treatment group(s), children and adults) separately.

The study population will consist of 60 children with Asthma (boys and girls, 8-17y/o) and 40 adults with Asthma (men and women, 18 yrs -35y/o) who: have been determined to be in good health by pre-participation sports physical performed at PERC, have no evidence of disease or disability that would impair participation in a vigorous physical activity program, have been diagnosed with persistent asthma according to criteria by NHLBI, have a clinical history of suggestive of exercise induced bronchoconstriction, have less than 50% fitness as determined from our own normative data collected in our lab (N=95), and with BMI percentile < 95th.

The control groups will be age, gender, and fitness matched with asthmatic participants, and consist of 60 children (boys and girls, 8-17yrs) and 40 adults (men and women, 18yrs -35y/o) who have been determined to be in good health by preparticipation history and physical examination performed at PERC, have no evidence of disease or disability that would impair performance of cycle ergometer exercise, and BMI < 95th percentile.

3. Provide the **inclusion and/or exclusion criteria** for the proposed subject population, as applicable.

[ ] Not applicable – This is not a clinical investigation and/or the characteristics of the population sufficiently describe the proposed subject population.

**Inclusion criteria Subjects with Asthma**

- Determined to be in good health by preparticipation history and physical examination performed at PERC
- No evidence of disease or disability that would impair participation in a vigorous physical activity program
- Diagnosed with persistent asthma according to criteria by NHLBI
- Clinical history suggestive of exercise induced bronchoconstriction
- VO2max <55 ml O2/kg/min and habitual physical activity corresponding to lifestyles from sedentary to moderately physically active, with exclusion of intense physical training
- BMI less than 95th percentile

**Exclusion criteria for Subjects with Asthma**

- Asthmatic participants who experience more than **two** asthma attacks a week
- Asthmatic participants who have been admitted to the ER/hospitalized due to an asthma attack more than **two** times in the past month
- If there is any evidence that the participant (adult and child) or that the child's/family is unfamiliar with the bronchodilator or any other asthma medications.
- Use of illegal drugs or abuse of alcohol
- Other conditions that preclude exercise (such as neuromotor disease, heart disease, major endocrine abnormalities or any other condition that would prevent a child from participating in vigorous physical activity for a training program)
- Very high physical fitness (>55 ml O2/kg/min VO2max) or habitual physical activity, corresponding to an elite athlete training regimen.
- Pregnancy or breastfeeding

**Inclusion criteria for Control Subjects**

- Determined to be in good health by preparticipation history and physical examination performed at PERC.
- No evidence of disease or disability that would impair performance of cycle ergometer exercise.
- VO2max <55 ml O2/kg/min and habitual physical activity corresponding to lifestyles from sedentary to moderately physically active, with exclusion of intense physical training
- BMI less than 95th percentile

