### **NON-TECHNICAL SUMMARY**

Provide a non-technical summary of the proposed research project that can be understood by IRB members with varied research backgrounds, including non-scientists and community members. The summary should include a brief statement of the **purpose of the research** and **related theory/data supporting** the intent of the study as well as a brief description of the **procedure(s) involving human subjects**. *This summary should not exceed ½ page.*

The goal of this research is to determine whether 10-weeks of exercise training can benefit asthmatic children and young adults with a history of exercise-induced bronchoconstriction (EIB). Physical activity is a double-edged sword for children and adults with asthma. On the one hand, exercise is a common trigger of wheezing (EIA—exercise induced asthma), occurring in as many as 80% of affected individuals. On the other hand, exercise and fitness training seem to benefit asthma control. The underlying causes responsible for EIA remain unknown. We will, for the first time, test hypotheses focused on mechanisms of exercise training, asthma and Exercise Induced Bronchoconstriction that involve the genomic changes of circulating white blood cells. We will also study an exciting newly discovered aspect of gene expression regulation in the white blood cells known as epigenetics: a process that takes place when genomic changes happen as a result of exposure to the environment. Our study is based on emerging exciting new data from this and other laboratories demonstrating that (1) white blood cells play an important role in bronchoconstriction[1,2] in children, (2) gene and cytokine expression in circulating white blood cells are abnormal in asthma,[3,4] and (3) brief exercise may change genomic and inflammatory-profiles of these cells.[5-7] Each participant will undergo a training regimen. The participants will come to our lab up to three times before the beginning of the training program, and up to three times immediately at the end of the exercise program to perform Exercise Fitness Session and Exercise Challenge Sessions. The visits may occur in any order, depending on the availability of the laboratory and timing. In the Exercise Fitness Session, the participant will perform a standard exercise test to determine fitness and will perform a series of pulmonary function tests. In addition, the participants will have two DXA scans to determine body composition (prior to

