### **Training Sessions**

Training will continue in community venues and in the Pediatric Exercise Research Center with professional personal trainers with a minimum of Bachelor degree in a Wellness/Exercise Science related field, P.E teachers or personal trainers certified by an accredited fitness

organization such as ACSM, NSCA, NASM or ACE. The training sessions will occur three times a week up to 10 weeks, in small groups of 3-6 subjects.

Those who participate in this study will have been cleared to participate in all sports, including school P.E. and extramural sports such as club soccer and basketball. In schools, children with asthma must have a release form for the use of a bronchodilator use when needed. These medicines can be determined by school officials. Increasingly, schools are permitting students to carry medication themselves.

The parent/legal guardian of the child participant will be instructed to bring his/her child's bronchodilator with them to the exercise training session (for adult participants, they will be instructed to bring their bronchodilator to the exercise training session). Before each training session begins, the trainer will ensure that the participant has his/her bronchodilator readily available prior to beginning exercise activities. Should an exercise-induced bronchoconstriction episode occur, participants will be instructed to respond as they have been prescribed by their personal physician. If necessary, the trainer will contact 9-1-1. All personal trainers will be required to have completed CPR certification (BLS).

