8. Explain **how the overall target sample size was determined** (e.g., power analysis; precision estimation).

9. Demonstrate that the **target sample size will be sufficient** to achieve the study goal and should coincide with the statistical approach **described in Section 3B**.

10. **Sources and information** of assumed group effects and variability should be supplied (e.g., pilot data; data from related literature).

To accomplish our aims, we will recruit 70 asthmatics and 70 gender-, age- and fitness-matched controls (as noted, below the 50th percentile of appropriate normative data) to participate in the training course. Given an anticipated dropout rate (based on our experience in recruiting subjects in this region) of about 10-15%, we expect to have complete samples around 60 participants in each group of children. The power analyses were based on PASS 2008 (Hintze, J. (2008). NCSS, LLC. Kaysville, Utah. [www.ncss.com](http://www.ncss.com)).

For the adult groups we will recruit 50 asthmatics and 50 gender, age and fitness-matched controls. We expect to have complete samples around 40 participants in each group.

For the primary outcome in gene expression, we will include about 3000 probe sets belonging to functional pathways of interest in asthma and exercise, as described above and in the Preliminary Studies Section. After filtration, around 1000 to 2000 probe sets will be left for analysis. Table 3 in the Human Subjects Section shows the power and effect size that can be detected from microarray data using a 2-sided 2-sample t-test for a range of: (1) probe sets **to examine** and (2) significant probe sets **to detect** (with FDR at 0.05 level). With the same power, a smaller effect size can be detected with a larger sample size. Effect size is defined as the expected log-transformed group difference divided by the within-group standard deviation. Our previous data showed that about 5% of the probe sets have an effect size over 0.9.

Table 4 shows the power analysis for the secondary outcome variables (e.g., in Aim 1, leukocyte function; in Aim 2, change in exhaled NO after the exercise challenge). The effect size is defined as the expected group difference divided by the within-group standard deviation for 2-sample t-test and as the mean difference between before- and after-training divided by the standard deviation of the difference for paired t-test.

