## B. Recruitment Process

1. Based on the methods checked above, describe and provide **details of the recruitment process** (i.e. when, where, by whom and how potential subjects will be approached, e.g. screening medical charts, findings subjects during routine patient visits, etc.).
2. If you will recruit by mail, e-mail, or phone, explain how potential subjects' **contact information will be obtained**.
3. If active recruitment methods will be used (i.e., researchers will make direct contact with subjects for the purpose of recruitment), explain how the individual's **privacy will be protected**. *Note: This is not the same as confidentiality (see the [Privacy and Confidentiality](#) web page).*

Participants will be recruited through electronic ads, flyer distribution, and through other studies being conducted on campus. Specifically, electronic ads will be placed in the UCI E-mail list-server. Flyers and provision of direct information to potential subjects will take place in schools and asthma clinics, pediatric endocrinology clinics of the UCI Medical Center, the Children's Hospital of Orange County, Harbor-UCLA General Hospital, the Orange County Kaiser pediatric endocrinology practice, and local health associations such as Latino Health Access and P.A.D.R.E. Flyers will also be placed in the waiting room at the ICTS in Orange and at Hewitt Hall (main campus). Lastly, , personnel for other studies utilizing the same study population may be provided with flyers to hand to their participants and study participants can then call if they would like more information about this study.

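### Controls enter the same training program as the asthma group, but their disease and disability criterion is written for cycle ergometer exercise, and the exclusion for conditions that preclude training is missing from their list

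*Protocol*

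**What the plan says.** **Who trains.** The Non-Technical Summary states "Each participant will undergo a training regimen". Section 4A says "we will recruit 70 asthmatics and 70 gender-, age- and fitness-matched controls" and gives the purpose of that recruitment as "to participate in the training course". Section 11 gives all subjects the same six visits, three before and three after training. Section 3B compares the training effect between groups.

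**What the training is.** Section 3A (Training Sessions, Training Program, Table 1) describes three sessions a week for up to 10 weeks. They combine aerobic work (ergometers, treadmill, rowing, ball games) with resistance work (light weights, bands, push-ups, pull-ups). No separate program is given for controls.

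**Who may enter (Section 4B).** The asthma inclusion list requires "No evidence of disease or disability that would impair participation in a vigorous physical activity program". The control inclusion list requires "No evidence of disease or disability that would impair performance of cycle ergometer exercise". The population description at the start of Section 4B makes the same distinction. The asthma exclusion list adds "Other conditions that preclude exercise (such as neuromotor disease, heart disease, major endocrine abnormalities", and closes that line with any condition that would prevent vigorous activity in a training program. The control exclusion list has no such line.

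**Clearance.** Under Training Sessions, Section 3A says "Those who participate in this study will have been cleared to participate in all sports". This is not limited to one group and does not appear in either eligibility list.

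**The concern.** An eligibility criterion should match what the participant will be asked to do. The control criterion matches the cycle tests, while the controls' main exposure is a mixed program of up to 10 weeks led by trainers. The exclusion missing from the control list is tied by its own wording to training and not to asthma, so its reason applies to anyone who trains.

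Two things are at stake. The first is safety. A control whose condition is compatible with cycling, but not with the wider program, meets the written disease and disability criterion. The second is comparability. Controls are the reference for the two-sample comparisons in Aims 1 and 2, and the blood outcomes include glucoregulatory hormones and cytokines. A comorbidity exclusion applied to one group alone is a possible group difference that has nothing to do with asthma.

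**Working it through.** The plan states no figure on this point, so the check sets the texts side by side and then counts whom the wording governs.

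1. **Do controls do the training?** Yes. The summary says every participant trains, and Section 4A recruits the child controls for the training course. The adult sentence in Section 4A does not repeat that phrase. The summary, the identical six visits in Section 11 and the repeat testing of each subject after training in Section 3A cover adults too.

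2. **How much?** 3 sessions per week × up to 10 weeks = up to 30 sessions, which agrees with Table 1.

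3. **Criterion against activity.**
   - Asthma group: the criterion refers to a vigorous activity program, and the activity is the training. They match.
   - Controls: the criterion refers to cycle ergometer exercise, and the activity is the same training. They do not match.

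4. **Exclusion lists.**
   - Asthma: attack frequency, emergency or hospital admissions, unfamiliarity with medication, drugs or alcohol, other conditions precluding exercise, very high fitness, pregnancy or breastfeeding.
   - Controls: regular anti-inflammatory use, regular bronchodilator use, drugs or alcohol, very high fitness, pregnancy or breastfeeding.
   - The first three asthma items are specific to asthma and need no control counterpart. The line on other conditions is not specific to asthma, and it is the one that is absent.

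5. **What else screens controls?** Good health on history and physical examination, a VO2max limit, a habitual-activity limit and a BMI limit. The asthma inclusion list has all four in the same terms and still carries the training-specific criterion and exclusion.

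6. **Could the analysis absorb a difference?** Section 3B tests gene expression with two-sample t-tests under false discovery rate control. For leukocyte function, a secondary mixed model adjusts for possible confounders, with gender, BMI percentile and fitness as examples. Matching is on age, gender and fitness. Comorbidity is named in none of these.

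7. **How many people does the wording govern?** From Table 2, target controls are 30 + 30 + 20 + 20 = 100 of 200. Maximum controls are 35 + 35 + 25 + 25 = 120 of 240. The maximum includes screen failures and early withdrawals, so it does not count people who train. At target, total control exposure is at most 100 × 30 = 3,000 participant-sessions. That is all control training, not training by affected controls.

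**The case against.** The case on the other side has real weight.

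- **Good health.** Controls are described as the healthy group and must pass a history and physical examination. A control with heart disease or a major endocrine abnormality would not easily be called healthy. Asthma participants have a chronic disease by definition, which is a natural reason to spell out further conditions for them. This stands in large part. It does not explain why the control criterion names a different activity from the one controls undertake.
- **The cycle tests are demanding.** The ramp test runs to the limit of tolerance, with heart rate and ECG monitored, and the challenge is ten 2-minute bouts at about 70% of peak work rate. Table 1 places both before training starts. A condition that impairs heavy cycling would therefore fall within the control criterion. What is left is conditions compatible with heavy cycling, but not with ball games or resistance work, and missed at examination. That may be a narrow set.
- **All-sports clearance.** If the sentence under Training Sessions binds controls, it closes most of the gap in practice. It then conflicts with the narrower eligibility wording, and the two must be reconciled.
- **Safeguards in training.** An on-call physician, CPR-certified trainers, stopping on discomfort and some sessions at the research center all reduce the risk.

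A reader might infer more than the documents support. It would be wrong to say that controls are screened only for the ability to pedal, given the examination and the other limits. Section 5B lists "pediatric endocrinology clinics of the UCI Medical Center" among the recruitment sites, which might suggest that controls with endocrine disease are expected. The section lists sites for the whole study, does not say which group is sought there, and a flyer does not confer eligibility. Nor do the documents show that Aim 1 is in fact biased: they give neither the number of affected controls nor a direction. Multiplying the 120 maximum controls by 30 sessions would also mislead, because screen failures do not train.

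**Conclusion.** The mismatch is real and can be read directly from the text. Controls undergo the training, their disease and disability criterion describes the test, the exclusion for conditions precluding training is one-sided, and no rationale is stated. The all-sports sentence and the control criterion cannot both be the operative rule as written.

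The wording governs half the study. The number of controls who would actually be admitted wrongly is not known and may be small, because the good-health examination should catch many of the same conditions. The conclusion assumes that the eligibility lists in Section 4B, and not a sentence in the procedures, are what staff will apply at screening. It is worth correcting because it touches both safety and comparability and costs almost nothing. It does not show that the planned comparison is invalid.

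**What to change.** Reconcile three places in Section 4B (the control population description, the control inclusion list and the control exclusion list) with the training described in the Non-Technical Summary, Section 3A and Section 4A. Both groups should be screened for the training program on the same basis. State in the eligibility lists whether the all-sports clearance under Training Sessions applies to both groups.

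The asthma group's own criterion and its line on other conditions offer ready wording. That line speaks of a child and would need adapting, since 40 of the 100 target controls are adults. The exact criterion is for the investigators to decide. If the group difference is intended, give the reason.

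The cost is a few lines of text. Controls already have a history and physical examination, so no procedure is added. The downside is possibly a few more control screen failures.

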**Exclusion criteria for Control Subjects**

- Regular use of anti-inflammatory medications parenterally, orally, or as inhaled agents.
- Regular use of bronchodilators
- Use of illegal drugs or abuse of alcohol
- Very high physical fitness (>55 ml O2/kg/min VO2max) or habitual physical activity, corresponding to an elite athlete training regimen
- Pregnancy or breastfeeding

4. If **exclusion** is based on age, gender, pregnancy/childbearing potential, social/ethnic group, or language spoken (e.g., Non-English Speakers), **provide a scientific rationale.**

This study will be limited to Children aged 8-17 years and Young Adults aged 18-35. The choice of studying young children/adolescents is due to the lack of information regarding the effect of acute bout of exercise and exercise training, in this specific age group on leukocyte function, genomic, and epigenetic responses. Few studies have been performed on adults looking at some aspects that we cover in this study, but results may not apply to children/adolescents, who present marked differences with adults. The young adults are going to serve as a reference group to those in 8-17 age bracket.

The effects of DXA to an unborn fetus, should a female subject be pregnant, are unknown, therefore pregnant individuals will be excluded.

To ensure protection of the subjects rights and safety, consent and assent forms will be carefully explained to them and to their authorized representatives. The study team has extensive experience in working with children and adults. It is also explicitly stated in the consent forms that participation in this protocol is voluntary.

An equal number of male and female participants will be included in the asthmatic and healthy groups. Different ethnic/racial groups will be included attempting to reproduce their respective distribution within the Orange County population, as per the latest report from the US Census Bureau. English and Spanish speaking subject will be recruited.

## **SECTION 5: RECRUITMENT METHODS AND PROCESS**

### **A. Recruitment Methods**

Please check **all** applicable recruitment methods that apply to the study. Place an "X" in the bracket [ ] next to the recruitment method.

- [ ] This study involves no direct contact with subjects (i.e., use of existing records, charts, specimens)
- **Skip to Section 6.**

- [X] UCI IRB approved advertisements, flyers, notices, and/or media will be used to recruit subjects. ***Submit advertisements for IRB approval.***
- Passive Recruitment - Potential subjects initiate contact with the study team.
  - ***Complete Question 5B - Explain where recruitment materials will be posted.***

- [ ] The study team will recruit potential subjects who are unknown to them (e.g., convenience sampling, use of social networks, direct approach in public situations, random digit dialing, etc.)
- Active Recruitment – Researchers contact potential subjects.
  - ***Complete Question 5B.***

- [ ] The UCIMC Clinical Trials web page will be used. ***Submit the UCIMC Standard Research Recruitment Advertisement for IRB approval.***
- Passive Recruitment - Potential subjects initiate contact with the study team.
  - ***Skip to Section 6.***

- [ ] The study will be listed on [Clinicaltrials.gov](http://Clinicaltrials.gov). *Note: This is required for all clinical trials.*
- Passive Recruitment - Potential subjects initiate contact with the study team.
  - **Skip to Section 6.**

- [ ] The UCI Social Sciences human subject pool will be used. **Submit the Social Science Human Subject Pool Recruitment Advertisement for IRB approval.**
- Passive Recruitment - Potential subjects initiate contact with the study team.
  - **Skip to Section 6.**

- [ ] Study team members will contact potential subjects who have provided permission to be contacted for participation in future research studies.
- Active Recruitment – Researchers contact potential subjects.
  - **Complete Question 5B – Explain when and how these individuals granted permission for future contact; provide the IRB protocol numbers, if applicable.**

- [ ] Study team members will approach their own patients, students, employees for participation in the study.
- Active Recruitment – Researchers contact potential subjects.
  - **Complete Question 5B.**

- [ **X** ] Study team members will send UCI IRB approved recruitment materials (e.g., recruitment flyer, introductory letter) to colleagues asking for referral of eligible participants.\*
- Passive Recruitment – Potential subjects initiate contact with the study team or
  - Active Recruitment – Colleagues get permission from interested individuals to release contact information to researchers. Researchers contact potential subjects.
  - **For Active Recruitment, complete Question 5B.**

*\*Note: Additional requirements for using this recruitment method are included in the Protocol Narrative instructions.*

- [ ] Study team members will provide their colleagues with a UCI IRB approved introductory letter. The letter will be signed by the treating physician and sent to his/her patients to inform them about how to contact study team members.
- Passive Recruitment - Potential subjects initiate contact with the study team.
  - The IRB approved letter must be sent by the treating physician.
  - The study team does not have access to patient names and addresses for mailing.
  - **Skip to Section 6.**

- [ ] UCI study team members will screen UCIMC medical records to determine subject eligibility and approach patients directly about study participation.\*
- Active Recruitment – Researchers contact potential subjects.
  - **Complete Appendix T to request a partial waiver of HIPAA Authorization.**
  - **Complete Question 5B.**

*\* Note Additional requirements for using this recruitment method are included in the Protocol Narrative instructions.*

Other Methods: <indicate the recruitment method(s) here>

- **Complete Question 5B, as applicable.**

